4.7 Subject Pre-Screening

Subjects will be pre-screened to determine their initial eligibility and interest in a study. Pre-screening criteria indicated with an asterisk * in section 4.6 (Phase 1 & Phase 2) Inclusion/Exclusion imaging criteria are considered standard of care in stroke management. Asterisks in parentheses (*) indicate inclusion/exclusion criteria that can be evaluated at sites that routinely perform multimodal CT or MRI as they are considered standard of care in stroke management. Therefore, subject eligibility to pre-screening criteria can be evaluated without obtaining informed consent. Informed consent will be obtained once subject has satisfied pre-screening criteria. All subjects pre-screened and screened will be documented on the Screening/Enrollment log.

4.8 Informed Consent and Screening

Subject identification and eligibility will be determined by the PI or study team based on their clinical assessment of the potential subject while that patient is undergoing standard of care for their neurological condition.

Before participation in the study, candidates who may be eligible for the study will be provided with an informed consent according to 21 CFR 56 and 45 CFR 160-164 and guidelines of the Investigational Review Board of the institution at which the study is being conducted. Candidates will be given time to review the consent form and ask questions about the study. The investigator will obtain written informed consent from the candidate. The candidate or legal representative must sign the consent form prior to enrolment. Candidates will also be required to sign a Health Insurance Portability and Accountability Act (HIPAA) form which includes a Privacy Rule. This rule gives special safeguards to Protected Health Information (PHI) that is identifiable or can be directly linked to the subject (e.g., social security number, name, birth date). This authorization may be part of the informed consent form or separate. If applicable to the investigator site location, candidates will also be required to sign the California Experimental Subject Bill of Rights.

A subject will be considered enrolled at the time of Informed Consent signature.

Potential subjects and/or their legal authorized representative / surrogate will be guided through the informed consent process by a member of the research team. This process includes informing the subject of the study procedures (in simple language), answering all questions, and obtaining written consent (Consent Form). The investigator or delegated study staff is responsible for obtaining written informed consent from each potential study participant. Informed consent should be obtained, when required, in written format and using a form approved by the local IRB. The subject must receive a copy of the signed and dated informed consent. Waivers of consent will not be utilized in this study.

A subject will be considered enrolled at the time of Informed Consent signature.

4.9 Randomization

Randomization will occur once subject has satisfied all inclusion/exclusion criteria and informed consent has been obtained. Subjects will be randomly assigned in equal number (1:1) to one of two procedure arms within each cohort: 1) TCD Exam or 2) No TCD Exam. The number of procedures and controls will be balanced within investigational sites, by baseline NIHSS severity (≤ 17 versus >17), age (<70 years versus ≥ 70 years at the time of randomization) occlusion location (M1 versus all other), and time of day of initial CT scan (0900-1700 and 1701-0859). Subject allocation to procedure will be accomplished by using an interactive web response (IWRS) or interactive voice response system (IVRS).

At the time of randomization, the site will access IVRS/IWRS and enter subject's screening NIHSS, age, occlusion location, and time of CT scan. Based on the information provided, the system will automatically generate the assigned treatment. If the site is unable to access website for randomization, an interactive voice response randomization is also available by phone.

4.10 Numbering of Study Subjects

Each site will be assigned a site number at the beginning of the study and each enrolled subject will be assigned a subject number. Subjects will be considered enrolled in the screening phase

when the informed consent has been signed and enrolled in the randomized phase when the randomization system (IVRS/IWRS) provides a treatment assignment. Site study coordinators will assign/obtain the subject number from the IVRS/IWRS and document the subject number on the screening/enrollment log once the subject has signed the informed consent. The subject number will consist of the study number and the site number followed by a sequential number that begins with "001". Site will also need to access the IVRS/IWRS to register the subject in the screening phase (detailed instructions on accessing the IVRS/IWRS will be provided in the user manual developed by the IVRS/IWRS vendor).

4.11 Screen Failures

Subject eligibility will be determined by the PI or study team based on their clinical assessment of the potential subject while that patient is undergoing standard of care CTA in the hospital.

For this protocol, a single measurement is defined as a collection of data at a single depth on a single side of the head. A scan is defined as a set of measurements which occur during a single data collection session and can include multiple measurements. A bilateral scan refers to measurements which are collected on each side of the head.

Subjects will be measured with TCD and the de-identified data will be reviewed to determine the quality of the data for analysis. Subjects will be considered screen failures if participant does not meet inclusion and exclusion criteria and if the device is unable to pass the registration process. At any point, the PI or research personnel can end the study.

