4.2 Study Endpoints

4.2.1 Phase 1 Study Endpoints

Phase 1 Primary Endpoint:

- Area Under the Curve (AUC), Sensitivity, and Specificity of VCI when compared against standard of care CTA imaging for large vessel occlusion assessment.

Phase 1 Secondary Technical Efficacy Endpoint:

- Area Under the Curve (AUC), Sensitivity, and Specificity of a novel machine learning (ML) algorithm when compared against standard of care CTA imaging for large vessel occlusion assessment.
- VCI and experimental ML algorithm compared to prehospital/neurological clinical scales for alternative diagnostic criteria.

Phase 1 Primary Safety Endpoint:

- Incidence of device-related serious adverse events
- Last Known Normal (LKN) to First Hospital Arrival (Initial Door-In) time
- Door to Initial CT imaging (non-contrast) time
- Door to IV-tPA time
- Door to Initial CTA Acquisition time
- Door to Groin Puncture time
- CTA Acquisition to Groin Puncture time

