4.15 Schedule of Assessments

Assessments	Phase 1 & 2 Schedule of Assessments			
	Cohort A¹ LVO TCD	Cohort B² Non-LVO TCD	Cohort C³ LVO NO TCD	Cohort D³ Non-LVO NO TCD
Informed Consent	X	X	X	X
Medical History	X	X	X	X
NIH Stroke Scale♦	X	X	X	X
Non-Contrast CT♦	X	X	X	X
CT Angiography♦	X	X	X	X
Cohort Assignment	X	X	X	X
Randomization TCD / No TCD	X	X	X	X
TCD Scan (NovaGuide or Lucid)	X	X		
Device-Related Adverse Events	X	X		
Concomitant Medications	X	X		

♦ Standard of Care

4. Cohort A LVO TCD subjects scans will be collected following CTA within a three (3) hour window, prior to treatment (e.g. mechanical thrombectomy).

5. Cohort B Non-LVO TCD subjects scans will be collected within a 24-hour period after enrollment.

6. If randomized to 'No TCD' group in either Cohort, TCD scan will not be conducted, but still followed through to discharge.

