4.16.1 NovaGuide System Scanning Technique

The scanning session will consist of an initial set-up and signal search (up to 20 minutes). During this time, the system will search for CBFV signals at depths between 45-65 mm. Once the signal is acquired, the system will monitor the signal for up to 20 minutes or until the PI or research teams end study.

The head cradle of the NovaGuide System is positioned underneath the subject's head and secured to a fixed location (bed, chair, or gurney). The user will affix two registration dots on each side of subject's temples. The subject's head is then positioned into the head cradle. The TCD modules are aligned to the head such that the probes are in contact with the subject's temples (temporal window). The user will register the Headmount to the subject's specific head shape and size. The user will apply gel to improve signal quality. The NovaGuide System will collect data and indicate to the user the scan status. The TCD operator will record the scan up to 20 minutes. Study measurements will not delay nor interfere with the patients' standard of care treatment as the PI or research team can end the study at any point.

Subjects will be evaluated during the scanning period per ALARA ("As Low As Reasonably Achievable") criteria. Scanning may not violate ALARA levels and will be immediately terminated if ALARA criteria reached during a scanning session.

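### Section 4.11 lists device registration failure as a screen failure, although by inference it can arise only after randomisation and in one arm; the groups assessed for adverse events also differ between sections

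*Combined protocol and SAP*

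**What the plan says.** Section 4.11 of the combined protocol and SAP makes subjects screen failures "if participant does not meet inclusion and exclusion criteria and if the device is unable to pass the registration process".

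On timing, section 4.9 states: "Randomization will occur once subject has satisfied all inclusion/exclusion criteria and informed consent has been obtained". Allocation is 1:1 to TCD or no TCD within each cohort. Section 4.10 treats a subject as "enrolled in the randomized phase when the randomization system (IVRS/IWRS) provides a treatment assignment". The schedule in section 4.15 places randomisation above the row "TCD Scan (NovaGuide or Lucid", which is marked for the two TCD groups only.

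Sections 4.2.1 and 4.2.2 list device-related serious adverse events and six workflow times, including "CTA Acquisition to Groin Puncture time", under the primary safety endpoint of each phase. Sections 11.1 and 11.2 compare the times with Cohorts C and D, the randomised no-TCD groups. Section 11.1 also plans three Phase 1 Get with the Guidelines percentages, computed only for subjects who have a NovaGuide measurement.

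On safety, the schedule marks "Device-Related Adverse Events" for both TCD groups. The closing paragraph of section 7 restricts assessment to subjects whose NovaGuide data are of adequate quality. Section 7.3 extends it to everyone scanned with NovaGuide.

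**The concern.** Screen failure normally means that a subject never entered the randomised comparison. A failed device set-up in a subject already assigned to TCD is a different event: it is an outcome of being in that arm. If sites or analysts drop such subjects, the TCD arm loses randomised members and the no-TCD arm cannot. The comparison is meant to show that adding the scan does not delay stroke care, and failed set-ups are among the cases it needs to include. Section 11 defines no analysis set that would keep them in.

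The adverse event wording raises a related problem. Whether a subject is assessed should not depend on whether the scan was readable, or on which of the two study devices was used.

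**Working it through.** **Step 1: when and in whom registration can fail.**
- Section 4.16.1 describes fitting the NovaGuide Headmount to the subject's head as part of the scanning session. No other device registration is described. The IVRS/IWRS step in section 4.10 registers a subject, not a device.
- Section 4.16.2 describes no registration step for manual Lucid M1 scanning.
- Cohorts C and D have no scan.
- Sections 4.9, 4.10 and 4.15 place randomisation before the scan.

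Registration failure can therefore arise only after randomisation, in TCD subjects scanned with NovaGuide. This is inferred; no sentence states it.

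**Step 2: effect on the workflow comparison.** Let f be the proportion of the TCD arm that fails registration, and S and F the mean time to puncture in the successes and failures. Omitting the failures changes the arm mean by

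S − [(1 − f)S + fF] = f(S − F).

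The documents do not give f. The sign of S − F is also open. A failed set-up uses time, but section 4.16.1 allows up to 20 minutes for set-up and search in any session, and then "Once the signal is acquired, the system will monitor the signal for up to 20 minutes" when the signal is found.

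**Step 3: which intervals are exposed.** Section 11.1 places device use after initial CT and IV-tPA, so two of its three percentages (IV-tPA and door to CT) are largely fixed before the device is applied. Door to puncture is not. The documents differ on CTA: section 11.1 has the device used while the subject waits for CTA or intervention, whereas section 4.16.2 has Cohort A scanned after CTA.

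**Step 4: effect on precision.** This uses the Hanley-McNeil standard error with n per group and AUC = A, where a = A/(2 − A) and b = 2A²/(1 + A):

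SE² = [A(1 − A) + (n − 1)(a − A²) + (n − 1)(b − A²)] / n²; bound = 1.645 × SE.

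The plan's own figures reproduce. A = 0.85 with 50 per group gives 1.645 × 0.0391 = 6.4 points (section 11.1: less than 7%). A = 0.90 with 150 per group gives 1.645 × 0.0185 = 3.0 points (section 11.2: 3%).

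Assuming equal loss in both cohorts:

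| Assumed loss | Phase 1 n per group | Bound, A = 0.85 | Phase 2 n per group | Bound, A = 0.90 |
|---|---|---|---|---|
| 0% | 54 | 6.2 | 156 | 3.0 |
| 2% | 52.9 | 6.2 | 152.9 | 3.0 |
| 5% | 51.3 | 6.3 | 148.2 | 3.1 |
| 10% | 48.6 | 6.5 | 140.4 | 3.1 |
| 20% | 43.2 | 6.9 | 124.8 | 3.3 |

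**Step 5: who is assessed for adverse events.**

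| Subject | Section 7, closing paragraph | Section 7.3 | Schedule 4.15 |
|---|---|---|---|
| Readable NovaGuide scan | yes | yes | yes |
| Unreadable NovaGuide scan | no | yes | yes |
| Failed registration, no scan | no | unclear | yes |
| Lucid scan only | no | no | yes |

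**The case against.** **The wording of 4.11.** Read strictly, the *and* requires both conditions, so an eligible subject whose registration fails is not a screen failure. Section 4.11 also never says that screen failures leave the analysis. Section 4.10 already puts an assigned subject in the randomised phase, and sections 11.1 and 11.2 already compare randomised groups. All of this stands, so it would go too far to infer that the plan orders the exclusion. It permits the exclusion and has no analysis set to prevent it. The exclusion for a physical limitation to placing the system (4.6.1.2, 4.6.2.2) overlaps with registration failure, but section 4.7 makes it a pre-screening item, so it does not cover a later failure.

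**A delay in minutes.** A reader might turn the session lengths in 4.16.1 into a bias of a given size, or one that favours the device. The documents do not support this. Sections 4.16.1 and 4.16.2 say that the measurements will not delay or interfere with care, and the team may stop at any point. Nothing bars a Lucid scan after a failed NovaGuide set-up, so such a subject need not be lost to the VCI analysis.

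**The NovaGuide denominator.** It is partly deliberate, since section 11.1 wants to describe the NovaGuide workflow. That justifies a supplementary summary. It does not justify using this denominator for the main result.

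**Missed serious events.** A reader might infer that serious device events would go unrecorded. Section 7 requires suspected NovaGuide-related events to be recorded from consent onward, and section 8 requires serious device-related events to be notified within one business day whatever the data quality. What remains is active assessment after failed or unreadable scans, and of Lucid subjects.

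**Device deficiencies.** Sections 4.18 and 8 would log some registration failures. They do not say that the subject stays in the arm or in the analysis.

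**Conclusion.** The point holds as a conflict of wording with a real consequence for analysis. Section 4.11 puts under screening an event that, by inference, belongs to the randomised phase of one arm. If the section is applied that way, the TCD arm of a primary safety comparison loses subjects after randomisation. The restricted percentages in section 11.1 have a similar effect, mainly for door to puncture.

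The size and direction of any bias cannot be stated, because the documents give neither a failure rate nor times by scan outcome. Precision is not the issue: even at an assumed 20% loss in both cohorts, the Phase 1 bound stays below the stated 7 points and the Phase 2 bound rises by about 0.3 to 0.4 points.

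The adverse event conflict is direct and needs no inference: three places name three groups. Its reach is limited, because suspected NovaGuide-related events and serious device-related events are already captured elsewhere.

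**What to change.** - **Section 4.11:** limit screen failure to ineligibility found before randomisation. Keep registration failures in their randomised arm as technical failures, and report their number by cohort.
- **Section 11:** state that workflow times and the section 11.1 percentages are analysed by randomised arm. A NovaGuide-only summary may stay as supplementary.
- **Sections 7 and 7.3:** reconcile both with the schedule in 4.15, so that adverse event assessment does not depend on data quality and covers both study devices.
- **Sections 11.1 and 4.16.2:** reconcile whether CTA comes before device use, so that it is clear which intervals the scan can affect.

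The cost is protocol wording and one table, with no additional patients.

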4.12 Study Discontinuation

4.12.1 Study Discontinuation by IRB

The IRB may choose to discontinue the study at any center(s) for which they granted approval if the:

- The research study is not conducted in accordance with the IRB requirements.
- The research study indicates unexpected serious harm to Subjects.

4.12.2 Study Discontinuation by Sponsor

The Sponsor may choose to discontinue the study should the Sponsor discover additional information during the study that may cause harm to subject safety.

If the study is terminated prematurely or suspended, the Sponsor will promptly inform all clinical Investigators of the termination or suspension and the reason(s) for this. The IRB/EC will also be informed, either by the Sponsor or Investigator if a local IRB/EC is utilized, promptly and provided with the reason(s) for the termination. If applicable, regulatory authorities will be informed.

4.13 Study Procedures

4.14 Imaging

Given the importance of imaging and quality of imaging to subject assessment, before and during the Study, the Sponsor will collaborate with participating centers to evaluate and optimize the quality of imaging and image transfer associated with the study.

4.15 Schedule of Assessments

Assessments	Phase 1 & 2 Schedule of Assessments			
	Cohort A¹ LVO TCD	Cohort B² Non-LVO TCD	Cohort C³ LVO NO TCD	Cohort D³ Non-LVO NO TCD
Informed Consent	X	X	X	X
Medical History	X	X	X	X
NIH Stroke Scale♦	X	X	X	X
Non-Contrast CT♦	X	X	X	X
CT Angiography♦	X	X	X	X
Cohort Assignment	X	X	X	X
Randomization TCD / No TCD	X	X	X	X
TCD Scan (NovaGuide or Lucid)	X	X		
Device-Related Adverse Events	X	X		
Concomitant Medications	X	X		

♦ Standard of Care

4. Cohort A LVO TCD subjects scans will be collected following CTA within a three (3) hour window, prior to treatment (e.g. mechanical thrombectomy).

5. Cohort B Non-LVO TCD subjects scans will be collected within a 24-hour period after enrollment.

6. If randomized to 'No TCD' group in either Cohort, TCD scan will not be conducted, but still followed through to discharge.

4.16 Scanning/Data Acquisition

The User Manual provided for the device details, in specific steps, the actions to be executed with the device for scanning/data acquisition. A general overview is provided below.

4.16.1 NovaGuide System Scanning Technique

The scanning session will consist of an initial set-up and signal search (up to 20 minutes). During this time, the system will search for CBFV signals at depths between 45-65 mm. Once the signal is acquired, the system will monitor the signal for up to 20 minutes or until the PI or research teams end study.

The head cradle of the NovaGuide System is positioned underneath the subject's head and secured to a fixed location (bed, chair, or gurney). The user will affix two registration dots on each side of subject's temples. The subject's head is then positioned into the head cradle. The TCD modules are aligned to the head such that the probes are in contact with the subject's temples (temporal window). The user will register the Headmount to the subject's specific head shape and size. The user will apply gel to improve signal quality. The NovaGuide System will collect data and indicate to the user the scan status. The TCD operator will record the scan up to 20 minutes. Study measurements will not delay nor interfere with the patients' standard of care treatment as the PI or research team can end the study at any point.

Subjects will be evaluated during the scanning period per ALARA ("As Low As Reasonably Achievable") criteria. Scanning may not violate ALARA levels and will be immediately terminated if ALARA criteria reached during a scanning session.

4.16.2 Lucid M1 System Scanning Technique (Traditional TCD)

If traditional TCD is conducted using the Lucid M1 System alone, measurements will be collected in the MCA at multiple depths ranges between 45 to 65 mm. The MCA scans will be collected from the trans-temporal window by positioning the probe superior to the zygomatic arch. Once cerebral blood flow velocity (CBFV) of the target vessel is found, the TCD operator will hold this position to record 30 seconds of data.

Cohort A TCD will be subjects identified per CTA findings in the Emergency Room (ER), Stroke Care Unit or Imaging Unit as having a large vessel occlusion. A single TCD scan will be collected by a designated TCD operator using the NovaGuide System or the Lucid M1 System alone (manual TCD). The TCD scan will be collected following CTA within a three (3) hour window and prior to standard of care stroke treatment (e.g., mechanical thrombectomy). Note, tPA can be administered prior to TCD measurements. Study measurements will not delay nor interfere with the patients' standard of care treatment. No follow-up scans will be collected.

Cohort B TCD will be subjects identified per CTA findings in the Emergency Room (ER), Stroke Care Unit or Imaging Unit as having a non-large vessel occlusion. A single TCD scan will be collected by a designated TCD operator using the NovaGuide Robotic System or the Lucid M1 System alone (manual TCD). These scans will be collected within a 24-hour period after enrolment and no follow-up scans will be collected.

Cohort C NO TCD will be subjects identified per CTA findings in the Emergency Room (ER), Stroke Care Unit or Imaging Unit as having a large vessel occlusion. No TCD scans will be conducted and subjects followed through to discharge.

Cohort D NO TCD will be subjects identified per CTA findings in the Emergency Room (ER), Stroke Care Unit or Imaging Unit as having a non-large vessel occlusion. No TCD scans will be conducted and subjects followed through to discharge.

4.17 ALARA Considerations

ALARA Considerations: "As Low As Reasonably Achievable – ALARA" principle for ultrasound to reduce the amount of total exposure to the subject without compromising exam quality.

Diagnostic ultrasound, including TCD, has been used clinically and in research for decades. In addition to the FDA guidance, there are several groups including the American Institute of Ultrasound in Medicine (AIUM), British Medical Ultrasound Society (BMUS), and the World Federation for Ultrasound in Medicine and Biology (WFUMB) that make recommendations on ultrasound safety for both fetal and non-fetal applications. These groups have focused on several areas of ultrasound safety including Thermal Index (TIC).

The FDA specifically references the AIUM for the ALARA recommendations for TIC and corresponding scan durations in the new guidance released in October 2017. Table 1 shows the recommended scan duration for a given TIC range. The ALARA recommendations are based on the TIC output by the device (which is displayed on the Lucid M1 System device at all times). TIC is defined as:

TIC – the thermal index for applications in which the ultrasound beam passes through bone near beam entrance into the body.

Thermal Index (TIC)	Recommended Duration (minutes)
>6.0	0
5.0-6.0	0.25
4.0-5.0	<1
3.0-4.0	<4
2.5-3.0	<15
2.0-2.5	<60
1.5-2.0	<120
<1.5	No Limit

Table 1 Recommended maximum exposure duration and TIC ranges (except the eyes which are not evaluated in this protocol)

If a subject meets ALARA criteria at any time during a scanning session, the scan will be discontinued.

